#### **Flow Sheet:**

Collect six blue tops

Run Quantra – One tube (Q1)

Mix 5 tubes = 15 ml

8 ml into four aliquot tubes and spin at 1000 rmp for 10 min.

One aliquot 1 ml for CL (1)

Balance 3.8 ml approx. for PP dilution.

Study protocol

7 ml of blood to 21 ml NS: 28 ml (Sample 2)

75% diluted sample:

3 ml Quantra – Q2

2m to aliquot tube for centrifuge CCL2 and transferred to CL2 (Draw from this CCL2 tube to fresh aliquot tube for CL2)

15% Reconstitution to diluted blood: NP Plasma (Sample 3)

4 ml DB + 0.7 (NP plasma) = 4.7

3ml Quantra Q3

1.7 ml CCL3 centrifuged and transferred to aliquot CL 3

15 % Reconstitution to diluted blood: PP Plasma (Sample 4)

4 ml DB + 0.7 PP =4.7

3ml Quantra Q4

1.7 ml centrifuged in CCL 4 and transferred to aliquot CL 4

30 % Reconstitution to diluted blood:NP Plasma (Sample 5)

4 ml DB + 1.7ml NP =5.7 ml

3 ml Qunatra Q 5

2 ml centrifuged in CCL5 and transferred to aliquot CL 5

30 % Reconstitution to diluted blood:PP Plasma (Sample 6)

4 ml DB + 1.7ml PP =5.7 ml

## 3 ml Qunatra Q 6

# 2 ml centrifuged in CCL 6 and transferred to CL 6

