### Methods:

### Details of the system:

The Quantra is a Point of the Care instrument where all components of test sequence, fluid handling, temperature control, ultrasound transmission, data processing and result output are automated. The device incorporates an embedded processor, a mechanical assembly that provides connection to a peristaltic pump and solenoid valves, heating elements to heat and maintain samples at 37°C, and ultrasound transducers operating in the megahertz range. Figure 1 shows the device used for the study. Quantra uses a plastic cartridge with embedded reagents. The cartridge has 4 test channels that perform 4 parallel and independent measurements using different reagent combinations in each channel. The cartridge has connection mechanism for attaching 3 ml syringe that can contain blood for coagulation analysis.

Channel	Reagents
1	Kaolin, calcium, buffers, and stabilizers
2	Kaolin, heparinase I, calcium, buffers, and stabilizers
3	Thromboplastin, polybrene, calcium, buffers, and stabilizers
4	Thromboplastin, polybrene, abciximab, calcium, buffers, and stabilizers

The reagents used in each channel are shown in the table 1.

The reagents in channel 1 are optimized for the measurements of Clot Time, whereas the channel 2 measures Clot Time without the effect of any potential heparin in the blood sample. Clot Times provides an indication of the functional status of the coagulation factors that lead to fibrin formation.

Furthermore, Clot Time and Heparinase Clot Time (channel 2) can be combined to a clot time ratio for determining the presence of residual heparin in the sample. Channel 3 is optimized to provide measurements of clot stiffness, which combines information about platelets and fibrinogen function. Finally, channel 4 is optimized to measure the Fibrinogen contribution to clot stiffness. Both channels 3 and 4 use hexadimethrine bromide to neutralize residual heparin. The difference between Channel 4 and 1 can provide platelet contribution to clot stiffness.

We designed an in vitro model of obstetric hemodilutional coagulopathy to assess the new technology. We also measured coagulation parameters after reconstituting the dilutional blood with undiluted blood to obtain serial increase in coagulation factors. The results obtained were compared to ROTEM®. The Quantra has been designed to provide results in 20 minutes, the fastest so far among available coagulation technologies.

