### Protocol:

Twenty healthy parturients aged 18-40 years with uncomplicated pregnancies at term gestation, 37 to 41 weeks, presenting for labor, or cesarean delivery will be recruited. Exclusion criteria includes hypertension, preeclampsia, gestational diabetes, preexisting coagulopathy, history of deep vein thrombosis, medications that impair coagulation, or history of pulmonary embolism or thrombosis. Women in active labor receiving intravenous fluids, or oxytocin will be also excluded. After obtaining consent, one table spoon of blood (16.2 ml) will be obtained at the time placement of intravenous cannula along with blood obtained for routine blood work (Hemoglobin and platelet count). The blood will be collected into five citrated Vacutainers (Beckton Dickinson, Franklin Lakes, NJ) each with a maximum capacity of 2.7 mL of blood and containing 0.5 mL 0.109 molar, 3.2% sodium citrated. Citrated blood from each Vacutainer from a single patient will be pooled to eliminate variability in citrate concentration between samples.

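### The flow sheet lists one fixed sample order with no rotation or timing rule, so if samples are run serially, PP versus NP and 30% versus 15% are aligned with sample age.

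*Combined protocol and SAP*

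**What the plan says.** The Flow Sheet section is a list of steps. It begins the testing with "Run Quantra – One tube (Q1", taken before the other five tubes are mixed. It then makes the diluted blood, "7 ml of blood to 21 ml NS: 28 ml (Sample 2", and continues in this order:

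- sample 3: "15% Reconstitution to diluted blood: NP Plasma (Sample 3"
- sample 4: "15 % Reconstitution to diluted blood: PP Plasma (Sample 4"
- sample 5: NP plasma at 30%
- sample 6: "30 % Reconstitution to diluted blood:PP Plasma (Sample 6"

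Here NP is non-pregnant plasma and PP is the woman's own plasma. Each sample is split between a Quantra run and the conventional laboratory tests (CL).

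The section on details of the system states "The Quantra has been designed to provide results in 20 minutes" and speaks of one instrument: "Figure 1 shows the device used for the study". The cartridge's four channels hold different reagent mixes, so one cartridge tests one sample.

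The Statistical Analysis text plans paired t tests of each parameter against baseline and an ANOVA across conditions. It has no term for run order or sample age. No section mentions rotation, a limit on time from draw to test, or recording of start times.

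**The concern.** The reconstitution part of the study asks what plasma source and plasma level do to the measured parameters. If blood or plasma changes while it stands, and PP is always tested after NP and 30% always after 15%, the change adds to or cancels those effects. Because the order is the same for every woman, no later analysis can separate linear drift from either main effect. An apparent difference between plasma sources, or an apparent response to level, could then be partly or wholly sample age.

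**Working it through.** The plan states no sample-size, power or alpha figure, so there is nothing of its own to reproduce.

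**Inputs from the documents.** There are 20 women (Protocol section: "Twenty healthy parturients aged 18-40 years with uncomplicated pregnancies at term gestation"). The listed positions are baseline 1, diluted 2, NP 15% 3, PP 15% 4, NP 30% 5 and PP 30% 6 (Flow Sheet).

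**Assumptions.** One analyser is used in listed order; each run takes 20 minutes, which the document gives as time to result and not as a slot length; drift is linear, at δ SD of the paired difference per slot; tests are two-sided at 5%.

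**Offsets between mean positions**

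| Contrast | Slots | Minutes at 20 per slot |
|---|---|---|
| PP − NP | (4+6)/2 − (3+5)/2 = 1 | 20 |
| 30% − 15% | (5+6)/2 − (3+4)/2 = 2 | 40 |
| Plasma-by-level interaction | (6−4) − (5−3) = 0 | 0 |
| Diluted − baseline | 2 − 1 = 1 | 20 |
| Samples 3, 4, 5, 6 − baseline | 2, 3, 4, 5 | 40, 60, 80, 100 |

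**False-positive rate when the true effect is nil.** For an offset of k slots, the paired t statistic has 19 df and non-centrality λ = δ × k × √20, with √20 = 4.472. The rate is the probability that its absolute value exceeds 2.093.

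| δ per slot | PP − NP (k = 1) | 30% − 15% (k = 2) | PP 30% − baseline (k = 5) |
|---|---|---|---|
| 0.05 | λ 0.224: 5.5% | λ 0.447: 7.1% | λ 1.118: 18.6% |
| 0.1 | λ 0.447: 7.1% | λ 0.894: 13.6% | λ 2.236: 56.5% |
| 0.2 | λ 0.894: 13.6% | λ 1.789: 39.7% | λ 4.472: 98.9% |

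The interaction stays at 5% throughout.

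**Rotating samples 3 to 6.** In a 4×4 Williams square with 20/4 = 5 women per sequence, each sample's mean position is (3+4+5+6)/4 = 4.5. The PP-NP and 30%-15% offsets fall to 0, the interaction stays at 0, and each ordered pair of neighbours occurs five times. Reconstituted minus baseline averages 4.5 − 1 = 3.5 slots (70 minutes). That equals the listed-order average, (2+3+4+5)/4 = 3.5, now shared equally by the four samples.

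**Rotating samples 2 to 6 instead.** The diluted sample's mean position becomes (2+3+4+5+6)/5 = 4, so its mean offset from baseline rises from 1 to 3 slots (60 minutes). At δ = 0.1 the false-positive rate of the unadjusted diluted-baseline t test rises from 7.1% to about 24%. With Q1 always first, a model with woman, sample and six-level position factors has 20 + 5 + 5 = 30 parameters but rank 29, because position 1 and baseline are the same cells. The four-sample model with four positions has 20 + 3 + 3 = 26 parameters and full rank.

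**The case against.** Serial running is inferred. The flow sheet gives no clock times and does not say that the listed order is the order on the analyser. The Protocol Methodology text names the PP aliquots before the NP ones. The number of analysers is not stated. Run in parallel, the offsets shrink towards zero. The drift size is also absent, so every rate above is conditional. All of this stands, and the point is worded accordingly.

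The Statistical Analysis text names tests against baseline and an ANOVA, with no explicit PP-NP or 30%-15% test. That is true. Those contrasts are nonetheless what the four reconstituted samples are arranged to show, and an ANOVA across conditions would include them.

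A reader might infer that sample age is confounded with every contrast. The documents do not support that. The plasma-by-level interaction has no net offset under linear drift. The stated aim, Quantra against conventional tests, compares portions of the same sample. Run order biases that comparison only if the two methods age differently or are tested at different times, and the timing of the CL tests is not given.

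A reader might also infer that rotating everything after Q1 is a free cure. It is not: it triples the mean age offset of the diluted sample from baseline, and a position factor then cannot recover the baseline contrasts.

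**Conclusion.** The point holds conditionally. The documents fix one listed order and give no rotation, timing rule or order term. If the samples are run serially in that order on one analyser, which is implied but not stated, PP versus NP is aligned with about 20 minutes of sample age and 30% versus 15% with about 40. Over the assumed drift range of 0.05 to 0.2 SD per slot, the inflation runs from negligible (5.5% for PP-NP) to serious (39.7% for 30%-15%). Which end applies cannot be known from the documents. The baseline contrasts carry offsets of 20 to 100 minutes on the same assumptions, and rotation does not cure them. The change is worth making because it removes the problem for the two main effects at almost no cost.

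**What to change.** State how many analysers are used and whether samples are run serially.

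Keep Q1 and Q2 where they are and rotate samples 3 to 6 over four sequences, five women each, with women allocated to sequences at random. One suitable set is 3-4-6-5, 4-5-3-6, 5-6-4-3 and 6-3-5-4.

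Record the draw time and the start time of every Quantra and CL test. Specify the analysis of these four samples as a repeated-measures model with woman, plasma source, level, their interaction and run position (four levels).

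Report the baseline contrasts with elapsed time shown. As a sensitivity analysis, a linear elapsed-time adjustment could be added, with its linearity assumption stated.

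The cost is a printed run schedule, one model term and slightly more care in labelling. The listed volumes suffice: of 28 ml diluted blood, sample 2 takes 3 + 2 = 5 ml and samples 3 to 6 take 4 × 4 = 16 ml, in any order. The plasma is spun before the blood is diluted, so the woman's own plasma is ready for any sequence, and the NP plasma needs only to be thawed by then. Rotation raises the mean age offset from baseline for samples 3 and 4 (from 2 and 3 slots to 3.5) and lowers it for samples 5 and 6 (from 4 and 5 to 3.5). If the samples are run in parallel on several analysers, rotation does no harm.

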Protocol Title: Evaluation of Novel Point of Care Coagulation System in Pregnant Women

Study No.: HP-00084317 Principal Investigator: [name] MD, [contact] NCT04301193 Sponsor: Hemosonics LLC

Dated: April 17, 2019

Evaluation of Novel Point of The Care Coagulation System in Pregnant Women

Unexpected obstetric hemorrhage continues to confront anesthesiologists, and obstetric hemorrhage spearheads as the leading cause of maternal mortality and morbidity. One of the hurdles confronting clinicians is the lack of a Point of the care coagulation system that can hasten the clinician management strategy in the right direction. Conventional time-tested coagulation systems take considerable time to obtain results. Thromboelastography (TEG®) and Rotational Throboelastometry (ROTEM®) are welcome additions to assess coagulation quickly. However, these two modalities require expertise and proficient training to perform test, and interpret results. This poses a hurdle for providing coagulation evaluation services around the clock. Therefore, many users of these technologies rely on the conventional laboratory personnel to use these technologies at remote location and thereby delaying expeditious acquisition of results by the clinicians. What is currently required for efficient and effective management of obstetric hemorrhage is a point of care coagulation system in the operating room or labor and delivery suite that is user friendly, easy and quick to perform by any clinician or support staff and does not require certified training. In this study, we evaluate a new point of the care, Quantra Hemostasis Analyzer system to assess coagulation rapidly with ease. The Quantra is a fully automated instrument that requires no sample handling steps from the user. The aim of the present study is to determine how Quantra system performs when compared to conventional coagulation tests at varying level of fibrinogen and clotting factors in the blood obtained from pregnant women.

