#### Protocol Methodology:

Three ml (aliquot 1) of pooled blood will be used analyzed in the Quantra analyzer using 4 channel cartridge for obtaining clot time and clot stiffness. Second aliquot (2) will be used to determine CBC and conventional coagulation tests ( PT, PTT, Fibrinogen, Factor VIII). These three sets (Quantra, CBC, and CL will provide baseline values for Quantra and conventional coagulation tests. 3 ml of pooled blood (aliquot 3) will be spun to yield plasma for additional process (PP).

Six ml (aliquot 4) will be mixed with 18 ml 0.9% normal saline to yield 24 ml of diluted blood (75%). Four ml will be used for Quntra and CL tests. Four additional aliquots of diluted blood sample will be mixed

with pregnant subject's plasma or non-pregnant plasma to yield 15%, and 30% PP aliquots, or 15% and 30% NP aliquots. These diluted blood enriched samples will be analyzed for Quantra and CL tests.

Details of the protocol flow are shown in table 2.

Statistical Analysis:

Results will be presented as Mean±SD for each parameter. Paired t test will be used to study differences in each parameter compared to the baseline for each method.

A scatter plot will be used to compare variations in parameter among three methods of coagulation assessment.

In addition, ANOVA (Analysis of Variance) for multiple comparisons will be used to assess changes in coagulation parameter of each methodology.

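### Plasma is added on top of already diluted blood, so cell content shifts along with clotting factors and channel 3 stiffness across samples 2 to 6 cannot be attributed to restored factors

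*Combined protocol and SAP*

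**What the plan says.** The stated aim is to see how Quantra performs against conventional tests "at varying level of fibrinogen and clotting factors in the blood obtained from pregnant women". The Flow Sheet first dilutes 7 ml of blood with 21 ml of saline (sample 2); Protocol Methodology gives 6 ml and 18 ml. Plasma is then added to 4 ml portions of this diluted blood (DB):

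- Samples 3 and 4 (15%): "4 ml DB + 0.7 (NP plasma) = 4.7" and "4 ml DB + 0.7 PP =4.7".
- Samples 5 and 6 (30%): "4 ml DB + 1.7ml NP =5.7 ml" and "4 ml DB + 1.7ml PP =5.7 ml".

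Details of the system describes channel 3 stiffness as reflecting platelets and fibrinogen jointly, channel 4 as the fibrinogen part, and clot time as reflecting the coagulation factors. A platelet contribution is derived by subtraction between channels.

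The same section says the reconstitution is done "to obtain serial increase in coagulation factors", but names undiluted blood as the reconstituting fluid. Protocol Methodology and the Flow Sheet use plasma.

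Protocol Methodology lists a complete blood count (CBC) for the baseline aliquot only. The mixes get Quantra and the conventional tests (CL). The analysis consists of paired t tests against baseline, scatter plots and ANOVA, with no term for platelets or haematocrit.

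**The concern.** The series is meant to raise clotting factors step by step and show whether Quantra follows. Because plasma is added to the diluted blood and does not replace saline, each step also changes the cell content. Quantra is run on the whole mix, whereas the conventional tests on samples 2 to 6 are run on centrifuged material and do not register that change.

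A weak rise in channel 3 stiffness from sample 2 to 3/4 to 5/6 could mean poor sensitivity to restored factors, or only a loss of cells. A strong rise in the PP samples could mean good sensitivity, or platelets carried over in the plasma. No volume-matched control, blood count on the mixes or adjustment is planned that would separate these. Recruiting more women would not help, because every woman's blood is mixed to the same recipe.

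**Working it through.** **Inputs.** From the Flow Sheet: 7 ml blood + 21 ml saline; v = 0.7 or 1.7 ml plasma added to 4 ml. Assumed, because the documents do not give it: haematocrit h = 0.30 to 0.40. Platelet retention r, the share of platelets left in the PP plasma, is unknown and is varied from 0 to 100%.

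**1. The plan's own percentages.** Dilution: 21/28 = 18/24 = 75%. Plasma share f = v/(4 + v): 0.7/4.7 = 14.9% and 1.7/5.7 = 29.8%, which reproduces the stated 15% and 30%. The alternative reading, v/4, gives 17.5% and 42.5% and does not match.

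**2. Whole-blood share.** 0.25 × (1 − f) gives 25.0% (sample 2), 21.3% (samples 3, 4) and 17.5% (samples 5, 6). Relative to sample 2: 4/4.7 = 0.851 and 4/5.7 = 0.702, so red cells are 15% and 30% lower with red-cell-free plasma. In absolute terms the loss is 3.7 and 7.5 percentage points. The two steps do not accumulate, since each mix starts from its own 4 ml.

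**3. Factor level in the plasma phase**, relative to the woman's own plasma (or NP plasma of equal strength):

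[(1 − f) × 0.25(1 − h) + f] / [(1 − f) × (0.25(1 − h) + 0.75) + f]

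At h = 0.35 this is 17.8%, 31.0% and 43.9%. Over h = 0.40 to 0.30 the ranges are 16.7–18.9%, 30.2–31.8% and 43.4–44.4%. Factors rise about 2.5-fold (43.9/17.8) while red cells fall by about 30%.

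**4. Platelets in the PP mixes**, as a percentage of undiluted blood: 0.25(1 − f) + f × r/(1 − h). Sample 2 is at 25.0%. At h = 0.35:

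| Platelets retained in PP plasma | Sample 4 | Sample 6 |
|---|---|---|
| 0% | 21.3% | 17.5% |
| 10% | 23.6% | 22.1% |
| 25% | 27.0% | 29.0% |
| 50% | 32.7% | 40.5% |
| 100% | 44.2% | 63.4% |

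The direction reverses at r = 0.25(1 − h): 15% at h = 0.40, 16.25% at 0.35 and 17.5% at 0.30. The Flow Sheet gives the PP plasma one ten-minute spin at a stated speed, with no g-force, rotor or residual platelet count, so the documents do not settle the sign.

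**5. Would holding every mix at 25% blood cure it?** Let c be the plasma platelet concentration relative to whole blood. Platelet drift is f(c − 0.25) now and f × c with the blood share held at 25%. The second is larger in size once c exceeds 0.125, that is, retention above 0.125(1 − h) = 7.5 to 8.75%. At 25% retention and h = 0.35, c = 0.25/0.65 = 0.385. The current series is 25.0, 27.0, 29.0%; the 25%-blood series would be 25.0, 30.7, 36.5%.

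**The case against.** The strongest reply has four parts.

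- **The method comparison survives.** Quantra and the conventional tests are run on the same mix, so the pairing within each sample is sound. This stands. A reader might infer that the mixing biases the whole comparison the study was set up to make; the documents do not support that. The aim concerns fibrinogen and factors, and the corresponding Quantra readouts are channel 4 and clot time, which the platelet argument reaches much less.
- **The direction is not known.** A reader might infer that platelets, and with them the platelet contribution, must fall in every mix. That holds for platelet-free plasma only and is not established for samples 4 and 6. This stands too. It removes the sign, not the confounding, and it adds a second problem: PP and NP mixes at the same level may differ in platelets.
- **The planned t tests are against baseline.** There the 75% saline dilution already lowers cells and factors together, and remixing samples 3 to 6 would not alter that. True, but the reconstitution series exists to be read across samples 2 to 6, and the ANOVA invites that reading.
- **Adding plasma to diluted blood is a legitimate model of hemodilution.** It is coherent, although the documents do not give it as a reason. This is why remixing is only an option. It does not make channel 3 interpretable as a response to factors alone.

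**Conclusion.** The concern holds for channel 3 stiffness and the derived platelet contribution along samples 2 to 3/4 to 5/6. The whole-blood share falls from 25.0% to 21.3% and 17.5% on the plan's own volumes; the 15% and 30% fall in red cells assumes red-cell-free plasma. Over the same steps factors rise about 2.5-fold, assuming h = 0.35 and PP plasma or NP plasma of equal strength. Platelets move down or up depending on an unreported carry-over, with the turning point at about 15 to 17.5% retention. The effect on stiffness itself cannot be sized, because the documents give no relation between platelet count and stiffness.

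Clot time, channel 4 and the conventional tests are less exposed, and the within-sample pairing is intact. A reader might also infer that holding the blood share at 25% removes the problem completely; it does so only with cell-free plasma, and above about 7.5 to 8.75% retention it enlarges the platelet drift.

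**What to change.** 1. **Restrict the conclusions.** State in the analysis section that conclusions about response to restored factors across samples 2 to 6 rest on clot time, channel 4 and the conventional tests. Report channel 3 and platelet contribution across the series as a combined cell and factor effect. Compare PP with NP on channel 3, at the same level, only if the PP plasma is shown to be platelet-poor.
2. **Measure the cells.** Run the CBC already used at baseline on each mix, to show the actual platelet and haematocrit levels. Samples 3 and 4 have no spare volume (3 + 1.7 = 4.7 ml), so either a little is taken before centrifugation or the mixes are made slightly larger. The Flow Sheet leaves 28 − (3 + 2 + 4 × 4) = 7 ml of diluted blood and about 3.8 − (0.7 + 1.7) = 1.4 ml of PP plasma unallocated.
3. **Reconcile the text.** Details of the system names undiluted blood as the reconstituting fluid; Protocol Methodology and the Flow Sheet use plasma. The difference matters: at the same volumes, undiluted blood would raise the whole-blood share from 25.0% to 36.2% and 47.4%.
4. **Optional, only with verified platelet-poor plasma.** Hold every mix at 25% blood, with plasma replacing saline: 1.175 + 0.70 + 2.825 = 4.7 ml and 1.425 + 1.70 + 2.575 = 5.7 ml (blood + plasma + saline). With 1.25 ml for a 5 ml sample 2, this needs 1.25 + 2 × 1.175 + 2 × 1.425 = 6.45 ml of blood. That is within the Flow Sheet's 7 ml but above the 6 ml in Protocol Methodology, so those volumes must be reconciled first.

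The cost of items 1 to 3 is a narrower channel 3 conclusion, a few added blood counts and a text correction. Item 4 adds separate pipetting of each mix and no longer mimics adding plasma to diluted blood.
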